4.5.7.4 Bleed Definitions and Reporting Definition of a Bleed

For the purpose of the efficacy analyses, a standardized definition of bleed, adapted from criteria defined by the Subcommittee on Standards and Criteria, FVIII/Factor IX subcommittee of the International Society of Thrombosis and Hemostasis, and similar to that used in a recent clinical study, will be used in this study (Blanchette et al. 2014; Mahlangu et al. 2014) as follows:

- An event is considered a treated bleed if coagulation factors are administered to treat signs or symptoms of bleeding (e.g., pain, swelling). An additional definition of all reported bleeds (irrespective of treatment with coagulation factors) will be applied for a separate analysis.
- Bleeds starting from the first sign of bleed and ending 72 hours after the last treatment for the bleed, within which any symptoms of bleeding at the same location or injections are ≤72 hours apart, are considered the same bleed.
- Any injection to treat the bleed, taken > 72 hours after the preceding injection, is considered the first injection to treat a new bleed at the same location.
- Any bleed at a different location is considered a separate bleed regardless of time from last injection.

Definition of Bleed Sites

Bleed sites are defined as follows:

Target joints: defined as a major joint (e.g., hip, elbow, wrist, shoulder, knee, and ankle) into which repeated bleeds occur (frequency of ≥ 3 bleeds into the same joint over the last 24 weeks prior to study entry) or as an unresolved target joint. An unresolved target joint is defined as a target joint that does not fulfil the criterion of ≤ 2 bleeds into this joint within a consecutive 12-month period (Blanchette et al. 2014).

Emicizumab—F. Hoffmann-La Roche Ltd 51/Protocol BO41423, Version 3

- Joint bleeds: defined as bleeds with bleed type "joint bleed" reported via the BMQ with at least one of the following symptoms:
 - Increasing swelling or warmth of the skin over the joint
 - Increasing pain
 - Progressive loss of range of motion or difficulty in using the limb as compared with baseline
- Muscle bleeds (sites as per the BMQ)
- Other (sites as per the BMQ)

Definitions of Bleed Types

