3.3.2.1 Bleed Rate

The efficacy of emicizumab is characterized by the number of bleeds over time. This will be calculated using a negative binomial (NB) regression model, which accounts for different follow-up times, with time that each patient stays in the study (efficacy period) included as an offset in the model. In addition, the number of bleeds will also be annualized for each patient using the following formula:

Annualized bleed rate (ABR) = (Number of bleeds/number of days during the efficacy period) \times 365.25.

The mean and median ABR based on the above formula using the observed numbers of bleeds instead of the number resulting from the model will also be calculated. In the case where the negative binomial model does not converge, the alternative derivations of the ABR will be used as the sole method of analysis.

ABR corresponding to treated bleeds, all bleeds, treated joint bleeds, treated target joint bleeds, and treated spontaneous bleeds will be analyzed in a similar manner. These will be summarized for all patients and listed for each patient individually. Several exploratory analyses will be conducted to characterize the type, location, and frequency.

3.3.2.1.1 72-Hour Rule:

Two bleeds of the same type (e.g., "joint", "muscle", or "other") and at the same anatomical location are considered to be one bleed if the second bleed occurs within 72 hours from the last treatment for the first bleed. The last treatment is defined as the last treatment before a new bleed occurs, either in the same or in a different location.

Bleeding rates and characteristics of bleeding describing location and type will also be provided using the 72-hour rule.

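### The SAP's 72-hour rule contradicts the protocol's bleed definition at one point, and the SAP does not say which rule produces the primary treated-bleed count

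*SAP*

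**What the plan says.** Protocol 4.5.7.4 introduces its counting rules with "For the purpose of the efficacy analyses, a standardized definition of bleed". A bleed is a treated bleed when coagulation factor is given for it. The rules are:

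- Window: "Bleeds starting from the first sign of bleed and ending 72 hours after the last treatment for the bleed".
- Link within the window: "any symptoms of bleeding at the same location or injections are ≤72 hours apart, are considered the same bleed".
- Split: an injection more than 72 hours after the one before it "is considered the first injection to treat a new bleed at the same location".
- Other sites: "Any bleed at a different location is considered a separate bleed regardless of time from last injection".

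SAP 3.3.2.1 sets out the negative binomial model and the per-patient ABR for treated bleeds and the other bleed endpoints. It neither defines a treated bleed nor cites protocol 4.5.7.4, and the protocol synopsis attached to the SAP does not contain the definition.

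SAP 3.3.2.1.1 then gives a 72-hour rule. It begins "Two bleeds of the same type", also requires the same anatomical location, and merges the second bleed into the first if it starts within 72 hours of the first bleed's last treatment. It adds: "The last treatment is defined as the last treatment before a new bleed occurs, either in the same or in a different location". The subsection closes with "Bleeding rates and characteristics of bleeding describing location and type will also be provided using the 72-hour rule". SAP 3.8 imputes missing times so that the rule can be run, but does not say for which analyses.

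**The concern.** The main efficacy result is a rate built on a count, so the rule that joins or separates reports is part of the endpoint. Two things looked wrong.

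First, the SAP's merge rule is not the protocol's. Under the protocol, the clock for a knee bleed runs from the last treatment of that knee bleed, and an elbow bleed is simply a separate event. Under the SAP, the elbow bleed freezes the knee's last treatment at whatever was given before the elbow bleed began.

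Second, the word *also* in the SAP's closing sentence can mean that the merged rates are an extra output, with the primary model run on entries as reported. It can equally mean that the rule applies throughout. A programmer working from the SAP cannot tell which.

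At stake is whether the reported ABR matches the protocol's endpoint and can be reproduced. SAP 3.3 makes the study descriptive, so no test or error rate is involved.

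**Working it through.** **Inputs.** The rules are those of protocol 4.5.7.4 and SAP 3.3.2.1.1. The annualization is that of SAP 3.3.2.1: bleeds divided by days in the efficacy period, times 365.25. Group sizes come from the sample-size sections (70 in all, 50 moderate, 20 mild) and from the protocol's aim of at least 5 female patients. The documents state no figure that depends on the counting rule, so there is none to reproduce. The sequences below are hypothetical.

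**The direct conflict.** The knee is treated on days 0, 2 and 3, an elbow bleed starts on day 1, and the knee is reported and treated again on day 5.

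- Protocol: the last knee treatment is day 3. The gap is 5 − 3 = 2 days = 48 h, which is ≤72 h, so there is one knee bleed.
- SAP rule: the last treatment before the new (elbow) bleed is day 0. The gap is 5 − 0 = 5 days = 120 h, which is >72 h, so there are two knee bleeds.
- SAP rule without the other-location cut-off: the last treatment is day 3 and the gap is 48 h, so there is one knee bleed.

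The cut-off alone makes the difference. Whether the elbow bleed is treated does not matter, because the SAP refers to any new bleed. The difference needs three things: further treatment at the first site after the other bleed starts; a repeat report more than 72 h after the last treatment before that start; and the same repeat no more than 72 h after the last actual treatment.

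**Counts under the three possible rules.**

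| Sequence | Protocol | SAP rule as written | Entries as reported |
|---|---|---|---|
| Knee/elbow sequence above, knee bleeds | 1 | 2 | 2 |
| Same site reported and treated again 48 h after treatment | 1 | 1 | 2 |
| Same site reported and treated again 120 h after treatment | 2 | 2 | 2 |
| One entry, injections 96 h apart | 2 | 1, or 2 if the protocol fills the SAP's silence | 1 |
| Knee signs untreated at 0 h, reported again and treated at 48 h: treated bleeds | 1 | 1 | 1 |
| Same sequence: all bleeds | 1 | 2, or 1 if the protocol fills the SAP's silence | 2 |

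The second row shows why the role of the rule matters more widely than the elbow case. In this simple sequence protocol and SAP agree, but an unmerged count gives one bleed more. The last three rows concern clauses that the SAP leaves out.

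**Size of one miscounted bleed.**

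- Patient ABR at 52 weeks: 365.25 / 364 = 1.003.
- Patient ABR at 24 weeks: 365.25 / 168 = 2.174.
- Shift of a group mean with equal follow-up = patient shift / n:

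| Group | n | 52 weeks | 24 weeks |
|---|---|---|---|
| All | 70 | 0.014 | 0.031 |
| Moderate | 50 | 0.020 | 0.043 |
| Mild | 20 | 0.050 | 0.109 |
| Female | 5 | 0.20 | 0.43 |

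The sequences move the count in both directions, so no net direction follows. The documents do not say how often they occur.

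**The case against.** The strongest reply is that the protocol governs anyway. Its definition is written for the efficacy analyses, and protocol 6.5.1 and 6.5.2.1 tie the primary and secondary bleed endpoints to it, though with the wrong section number. The SAP nowhere says that it replaces it. Placing the 72-hour rule under Bleed Rate, and imputing times so that it can be run, both suggest that it is the working derivation. The conflicting sequence is narrow, the overall effect of one bleed is small, and the SAP already warns against over-reading small subgroups.

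Much of this stands, and it rules out three stronger readings.

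- A reader might infer that the SAP contradicts the protocol in several clauses. The missing split for injections more than 72 h apart and the missing symptom link are omissions. The SAP's text is a rule for merging two bleeds, and where it is silent the protocol can still apply.
- A reader might infer that the same-type condition changes counts. It does so only if the bleed questionnaire (BMQ) can record one location under two types. Protocol 4.5.7.4 lists joint, muscle and other as bleed sites, and the documents do not show how the BMQ codes them.
- A reader might infer that the primary count is definitely unmerged. No section names entries as reported as an analysis, and that reading rests on the word *also*.

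The reply does not reach the other-location cut-off. There the SAP is not silent: it states a rule that gives a different count from the protocol's. If the protocol governs, the SAP should say so and not carry a rule that contradicts it.

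**Conclusion.** The point holds as one direct conflict plus an unstated governing rule. The other-location cut-off contradicts protocol 4.5.7.4 and can turn one bleed into two. The SAP also leaves open whether the primary treated-bleed count is merged, which changes even a simple 48-hour repeat.

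Each miscounted bleed is worth about 1.00 on a patient's ABR at 52 weeks and about 0.014 on the mean of 70. The group figures assume equal follow-up. SAP 3.3.1 runs each patient to cut-off or withdrawal, so actual shifts will differ. The larger shifts belong to small groups or to 24 weeks of follow-up.

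The documents do not support a claim that the reported ABR will be materially wrong or biased in a known direction. This should be fixed before the bleed derivation is programmed, for accuracy and reproducibility, with no consequence for any test.

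**What to change.** In SAP 3.3.2.1, state that the primary negative binomial model, the ABR and the secondary bleed counts all use the protocol 4.5.7.4 definition, including the split at an injection more than 72 h after the preceding one. Then:

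- Remove the other-location cut-off from SAP 3.3.2.1.1 or reconcile it with the protocol. State how a factor dose is linked to a bleed when two bleeds are open.
- State a convention for the symptom link where symptoms are not collected, for example the reported bleed start. SAP 2.2.1 limits symptom data to muscle and joint bleeds in patients aged 12 or over.
- Say what the same-type condition is for. It need not be deleted if location coding makes it redundant.
- Label any count of entries as reported, or by another rule, a sensitivity analysis.
- Editorial: the references to 4.5.7.3 in protocol 6.5.1 and 6.5.2.1 should read 4.5.7.4.

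The cost is SAP wording, the editorial protocol correction and one derivation program. The BMQ already collects location, bleed start and treatment times, so no new data collection should be needed. This assumes that its records allow doses to be assigned to individual bleeds, which protocol 3.1 suggests but the documents do not fully show.

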3.3.2.2 Health-Related Quality of Life (HRQoL)

For CATCH questionnaire, descriptive analyses including summaries and 95% confidence intervals of change from baseline for each individual subscale will be performed. Patient compliance with the CATCH will be summarized at each assessed timepoint.

For the EmiPref patient preference questionnaire, the proportion of patients/caregivers preferring either emicizumab after 17 weeks of treatment or previous hemophilia treatment regimen will be presented with 95% CIs. The proportion of patients selecting each reason for their preference and the top three preferred reasons affecting the patient preference will also be summarized. Patient/caregiver compliance with the EmiPref will be summarized for Week 17.

Emicizumab —F. Hoffmann-La Roche Ltd 11/Statistical Analysis Plan BO41423 Summary statistics of the number and proportion of days away from school/work and days hospitalized will be presented.

3.3.2.3 Joint Health and Physical Activity

The Hemophilia Joint Health Score (HJHS) measures joint health of the joints most commonly affected by bleeding in hemophilia. The HJHS 2.1 provides joint specific total scores which is added to obtain the sum of joints totals and also a global gait score. These two scores are then added to obtain HJHS total score. For the HJHS, descriptive analyses will be presented by timepoint. All enrolled subjects who contribute to valid activity data will be analyzed for activity.

Relative change from baseline (Weeks 1–2 period) at Weeks 13 (Weeks 12–13 period), 25 (Weeks 24–25 period), 37 (Weeks 36–37 period), and 49 (Weeks 48–49 period) in mean MVPA and DSC will be calculated and summarized. Subject-level data will also be presented at each timepoint.

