6.5.2.1 Bleed Endpoints

The clinical effect of prophylactic emicizumab on the secondary bleed endpoints of all bleeds (i.e., those treated and untreated with coagulation factors), joint bleeds, target joint bleeds, and spontaneous bleeds (see Section 4.5.7.3 for bleed definitions) will be analyzed in the same manner as for the primary analysis.

The number of bleeds, sites of bleeds, and types of bleeds will be summarized for all patients and listed for each patient individually. Several exploratory analyses will be conducted to characterize the type, location, duration, frequency, and pattern of bleeds. For continuous endpoints, descriptive statistics will be calculated and categorical endpoints will be characterized through frequency tables.

6.5.2.2 Health-Related Quality-of-Life, Patient Preference, Joint Health, Activity, Menstruation Heaviness, and Menstruation-Related Quality of Life

With regards to the PRO secondary objectives, scores by each domain for the CATCH will be computed for each assessment with changes in scores examined for the assessments over time, and these will be summarized descriptively. Patient compliance with the CATCH will be summarized at each assessed timepoint.

For the EmiPref, the proportion of patients/caregivers preferring emicizumab after 17 weeks of treatment will be presented along with the reasons for that choice. Patient/caregivers compliance with the EmiPref will be summarized for Week 17.

For the activity assessment and HJHS, descriptive analyses will be presented by timepoints. All enrolled subjects who contribute to valid activity data (e.g., at least 8 days of wearing the device within a 14-day observation period) will be analyzed for

Emicizumab—F. Hoffmann-La Roche Ltd 79/Protocol BO41423, Version 3

activity. The definition of valid activity data and the handling of missing values will be provided in the SAP.

Relative change from baseline (Weeks 1–2 period) at Weeks 13 (Weeks 12–13 period), 25 (Weeks 24–25 period), 37 (Weeks 36–37 period), and 49 (Weeks 48–49 period) in mean MVPA and DSC will be calculated and summarized. Subject-level data will also be presented at each timepoint.

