2.5 ANALYSIS TIMING

An interim analysis and the subsqueent primary analysis will be performed after all 50 patients with moderate hemophilia A have completed respectively 24 weeks of emicizumab treatment and 52 weeks of emicizumab treatment, or are lost to follow-up, or have withdrawn, whichever occurs first.

The final analysis will occur at the end of the study. Additional updates may be performed between the primary and final analysis as might be requested by Health Authorities or deemed necessary by the Sponsor.

3. STATISTICAL METHODS

For continuous variables, means, medians, ranges, and standard deviations will be presented. For categorical variables, the number and percentage of patients within each category will be presented. For each variable (continuous or categorical), the number of available observations will be reported. No formal hypothesis testing will be performed as the study is entirely descriptive.

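### Activity change is specified only as relative change from baseline; its arithmetic mean, if taken per patient, is biased upward under no true change and has no value at zero baseline MVPA

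*SAP*

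**What the plan says.** Activity compared with baseline is a secondary efficacy endpoint (protocol 2.2.2, SAP 2.3.2). Patients aged 5 years or older wear a wrist accelerometer for five 14-day periods, the first being Weeks 1–2 (protocol 4.5.8, SAP 2.2.3).

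The analysis sentence is the same in SAP 3.3.2.3 and protocol 6.5.2.2. It begins "Relative change from baseline (Weeks 1–2 period) at Weeks 13 (Weeks 12–13 period", goes on to Weeks 25, 37 and 49, and ends "in mean MVPA and DSC will be calculated and summarized". Both documents add: "Subject-level data will also be presented at each timepoint". Neither gives a formula, says whether the mean is a patient's period mean or the group mean, or covers a baseline at or near zero.

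The opening of SAP section 3 fixes the statistics: "For continuous variables, means, medians, ranges, and standard deviations will be presented". It also says: "No formal hypothesis testing will be performed as the study is entirely descriptive".

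Protocol 6.5.2.2 plans one further summary: "For the activity assessment and HJHS, descriptive analyses will be presented by timepoints". The matching sentence in SAP 3.3.2.3 names the HJHS only. The protocol gives as an example of valid data "at least 8 days of wearing the device within a 14-day observation period", and then defers: "The definition of valid activity data and the handling of missing values will be provided in the SAP". SAP 3.3.2.3 uses the term valid activity data without defining it, and SAP 3.8 on missing data deals only with bleed and treatment entries.

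**The concern.** A ratio of two noisy measurements is not symmetric. A baseline that is low by chance inflates the ratio more than an equally high one deflates it, so individual ratios average above 1 when true activity is constant. The smaller the baseline, the worse the effect. MVPA can be very low in patients with joint disease, and at zero the ratio does not exist.

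The error points in the drug's favour, and a single-arm study has no control group in which the same drift would show up. If a patient has zero baseline MVPA, someone must decide after seeing the data whether to drop, impute or offset that value.

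**Working it through.** The documents state no SD, expected change or precision for activity, so there is no planned figure to reproduce. The check asks what the planned mean would show if nothing changed.

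**Inputs from the documents:** relative change (SAP 3.3.2.3); mean and median both reported (SAP section 3); 8 to 14 valid days per period (protocol 4.5.8 and 6.5.2.2); about 70 patients (SAP 2.4), fewer for activity because children under 5 do not wear the device. **Assumed, shown as ranges:** within-patient log SD s of a period mean, day-to-day CV, correlation between period errors, share of days with zero MVPA.

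**Step 1. Bias of the mean.** Let X and Y be one patient's baseline and follow-up period means, with the same true level and independent errors. Then E[Y/X] − 1 = E[Y]·E[1/X] − 1, which is above 0 by Jensen's inequality. For log-normal errors it equals exp(s²) − 1, and the median of Y/X − 1 is 0.

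| s | exp(s²) − 1 | median |
|---|---|---|
| 0.1 | +1.0% | 0 |
| 0.2 | +4.1% | 0 |
| 0.3 | +9.4% | 0 |
| 0.4 | +17.4% | 0 |
| 0.5 | +28.4% | 0 |

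Simulation agreed to within 0.1 percentage points.

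**Step 2. The same from daily data.** For gamma-distributed independent days with coefficient of variation CV, averaged over d days, the bias is 1/(d/CV² − 1).

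| daily CV | d = 14 | d = 8 |
|---|---|---|
| 0.5 | 1/(56 − 1) = +1.8% | 1/(32 − 1) = +3.2% |
| 1.0 | 1/(14 − 1) = +7.7% | 1/(8 − 1) = +14.3% |
| 1.5 | 1/(6.22 − 1) = +19% | 1/(3.56 − 1) = +39% |

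Slower variation between periods adds to this. Daily CV 1.0 over 14 days with a between-period log SD of 0.3 gave +17.9% in simulation.

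**Step 3. Correlated period errors.** The bias becomes exp(s²(1 − ρ)) − 1. At s = 0.3 it is +4.6% for ρ = 0.5 and +0.9% for ρ = 0.9.

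**Step 4. Visibility at trial size.** In 20,000 simulated trials of 70 patients with no true change, the mean relative change was above zero in 87.5% (s = 0.2), 95% (s = 0.3) and 99.5% (s = 0.5). An unbiased measure with symmetric error would give about half.

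**Step 5. A near-zero baseline.** One patient goes from 1 to 20 min/day and 69 stay the same. The individual relative change is (20 − 1)/1 = 19. The mean is 19/70 = 0.271, or +27%, and the median is 0. On the absolute scale the mean is 19/70 = 0.27 min/day.

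**Step 6. An exactly zero baseline.** Every valid day must be zero. With independent days and a zero-day share p, the probability is p^d. For p = 0.5 it is 0.4% (8 days) or 0.01% (14 days); for p = 0.8 it is 16.8% or 4.4%. This is plausible for MVPA in very inactive patients and unlikely for step count.

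**Step 7. Alternatives under no change.** Absolute change has expectation 0. The median relative change, the relative change of group means and the geometric mean ratio all stayed within 0.2 points of zero in simulation. Only absolute change and the ratio of group means need no rule for individual zeros, since a log ratio also fails at zero.

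**The case against.** The case against making much of this has five parts.

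- **The median is reported too.** It stays at zero under no change, and the range and SD would show outliers. A reader might infer that the activity table as a whole must show a spurious gain. The documents do not support that: only the mean is affected.
- **Relative change is not all that is planned.** A reader of the SAP alone might infer that it is. The protocol also plans activity summaries by timepoint, and both documents plan subject-level data. It is correct that no other change measure is specified.
- **The per-patient reading is not certain.** If the mean is the group mean, the ratio is neither undefined nor materially biased. Presenting subject-level data makes the per-patient reading natural, but the text does not settle it.
- **The size is unknown.** A period mean averages 8 to 14 days. A period-mean CV of 50% from independent daily variation alone needs a daily CV of 0.5 × √8 = 141% or 0.5 × √14 = 187%. Smaller values give only a few per cent, and correlation lowers the bias further.
- **Relative change is a defensible scale.** Ages from 5 years upward are pooled, so scaling to each patient's own level has a purpose, and the protocol specifies it. A reader might infer that it should be deleted; that does not follow.

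All five stand as limits on size and remedy. None removes the problem: SAP section 3 puts the arithmetic mean in the table, the documents leave the ratio undefined, and no rule covers a zero baseline.

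**Conclusion.** The point holds in a limited form. Relative change is the only change measure specified for MVPA and step count, and its arithmetic mean will be reported. If the ratio is formed per patient, that mean is biased upward under no true change, can be dominated by one near-zero MVPA baseline, and has no value for a patient with zero baseline MVPA.

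The bias runs from about 1% to over 30% across the assumed variabilities and is smaller if period errors are correlated. The documents supply no figure that would narrow this range. The result rests on the per-patient reading and on period errors that are not strongly correlated. The near-zero example and the undefined ratio at zero need no distributional assumption.

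The consequence is modest. Activity is a descriptive secondary endpoint with no test attached, and neither the primary endpoint nor any decision rule depends on it. The change is still worth making, because the artefact favours the drug in a study without a control group and is almost free to remove.

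**What to change.** In SAP 3.3.2.3, with matching wording in protocol 6.5.2.2:

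- Make absolute change from the Weeks 1–2 period (MVPA in min/day, steps/day) the lead summary, with mean, median and 95% CI. This fits the aim in protocol 3.3.7 of measuring change in the amount of activity. It also matches the SAP's own practice for CATCH, where change from baseline is summarised with 95% CIs (SAP 3.3.2.2).
- Keep relative change as supportive. Define the formula, and summarise it by the median or the ratio of group means (for step count, the geometric mean ratio is also suitable), not by the arithmetic mean of individual ratios.
- State how zero MVPA baselines are handled wherever individual ratios are shown.
- Restore the by-timepoint activity descriptives that the protocol plans and the SAP sentence omits.
- Supply the valid-data definition and missing-value rule that the protocol defers to the SAP.

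No new data are needed. The cost is a little more table work and a small wording alignment between protocol and SAP. Absolute change does not scale for age or usual activity level, which is why the relative measure is kept alongside it.
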